Grade 3	
Omit study treatment until resolved to ≤ grade 1, then resume nazartinib at the same dose level:
 
 
If resolved in ≤ 7 days, then resume capmatinib at same dose level
 
If resolved in > 7 days, then resume capmatinib ↓ 1 dose level
 
If recurrence of grade 3 toxicity during nazartinib monotherapy, omit study treatment until resolved to ≤ grade 1, then resume nazartinib at ↓ 1 dose level
 
If no recurrence of grade 3 toxicity after 7 days of nazartinib monotherapy at ↓ 1 dose level, resume capmatinib at same dose level
 

Peripheral edema	
Grade 1 or 2	Maintain dose levels of nazartinib and capmatinib
Grade 3	
Omit study treatment until resolved to ≤ grade 1, then resume nazartinib at same dose level and re-evaluate after 7 days, or sooner if clinically indicated
 
 
If no recurrence of grade 3 toxicity after 7 days of nazartinib monotherapy, resume capmatinib at ↓ 1 dose level
 
If recurrence of grade 3 toxicity on maintained dose of nazartinib and ↓ 1 dose level of capmatinib, omit study treatment until resolved to ≤ grade 1, then resume capmatinib at ↓ 1 dose level and maintain dose level of nazartinib
 
If recurrence of grade 3 toxicity during nazartinib monotherapy, omit study treatment until resolved to ≤ grade 1, then resume nazartinib at ↓ 1 dose level
 
If no recurrence of grade 3 toxicity after 7 days of nazartinib monotherapy at ↓ 1 dose level, resume capmatinib at ↓ 1 dose level
 

Grade 4	Permanently discontinue capmatinib and omit dose of nazartinib until resolved to ≤ grade 1, then continue nazartinib monotherapy
Eye Disorders (Results and images of ophthalmic examinations should be made available upon request)	
Grade 1 or 2 Uveitis/Retinopathy	Maintain dose level of both study drugs, and refer to an ophthalmologist for ophthalmic monitoring at least every 14 days.
Grade 3 Uveitis/Retinopathy	
Omit study treatment until resolved to ≤ grade 1, and refer to an ophthalmologist for ophthalmic monitoring at least once a week, then:
 
 
If resolved in ≤ 14 days, then resume capmatinib at same dose level and nazartinib at ↓ 1 dose level
 
If resolved in > 14 days, then permanently discontinue participant from nazartinib and resume capmatinib at same dose level
 

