Grade 4 Uveitis/Retinopathy	
Permanently discontinue nazartinib and refer the participant to an ophthalmologist for monitoring. Resumption of nazartinib following resolution to ≤ grade 1 may be considered if approved by ophthalmologist and after documented discussion with Novartis.
 
Resume capmatinib at same dose level upon resolution to ≤ grade 1.

Retinal vein occlusion of any Grade	Permanently discontinue nazartinib and refer the participant to an ophthalmologist immediately for monitoring. Resumption of nazartinib following resolution to ≤ grade

Worst toxicity CTCAE a Grade (value)	Recommendation
	1 may be considered may be considered if approved by ophthalmologist and after documented discussion with Novartis. Resume capmatinib at same dose level upon resolution to ≤ grade 1.
Other ocular/visual toxicity	
Grade 1 or 2	Maintain dose levels of both drugs, and within one week refer to an ophthalmologist for ophthalmic monitoring at least every 14 days.
Grade 3	Omit study treatments until resolved to ≤ grade 1, and within one week refer to an ophthalmologist for ophthalmic monitoring at least once a week, then: 
 
• If resolved in ≤ 14 days, then resume capmatinib at same dose level and nazartinib at ↓ 1 dose level
 
• If resolved in > 14 days, then discontinue participant from nazartinib and resume capmatinib ↓ 1 dose level
 

Grade 4	Permanently discontinue nazartinib, omit capmatinib and refer the participant to an ophthalmologist immediately for monitoring. Resumption of nazartinib at ↓ 1 dose level following resolution to ≤ grade 1 may be considered if approved by ophthalmologist and after documented discussion with Novartis. Resume capmatinib at same dose level upon resolution to ≤ grade 1.
Other adverse events	
Grade 1 or 2	Maintain dose levels of nazartinib and capmatinib

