Grade 1 or 2	Maintain dose level, consider to initiate appropriate support medication. For any intolerable grade 2 (e.g. limiting instrumental activities of daily living), consider omitting the dose until resolved to ≤ grade 1, then resume either at same dose or ↓ 1 dose level.
Grade 3	Omit dose until resolved to ≤ grade 1, then resume at ↓ 1 dose level
Grade 4	Permanently discontinue capmatinib

All dose modifications should be based on the worst preceding toxicity.
 
a Common Toxicity Criteria for Adverse Events (CTCAE version 5.0).
 
b “Combined” defined as: total bilirubin increase to the defined threshold concurrently with ALT/AST increase to the defined threshold
 
c “Cholestasis” defined as: ALP elevation (> 2.0 x ULN and R value (ALT/ALP in x ULN) < 2.0) in participants without bone metastasis, or elevation of ALP liver fraction in participants with bone metastasis
 
d If combined elevations of AST or ALT and total bilirubin do not meet the defined thresholds, please follow the instructions for isolated elevation of total bilirubin and isolated elevation of AST/ALT, and take a conservative action based on the degree of the elevations (e.g. discontinue treatment at the situation when omit dose is needed for one parameter and discontinue treatment is required for another parameter). After all elevations resolve to the defined thresholds that allow treatment re-initiation, re-start the treatment either at the same dose or at one dose lower if meeting a criterion for dose reduction
 
* Note: If total bilirubin > 3.0 x ULN is due to the indirect (non-conjugated) component only, and hemolysis as the etiology has been ruled out as per institutional guidelines (e.g., review of peripheral blood smear and haptoglobin determination), then ↓ 1 dose level and continue treatment at the discretion of the investigator
 
** Note: antidiarrheal medication is recommended at the first sign of abdominal cramping, loose stools or overt diarrhea
 
*** During the whole duration of treatment with capmatinib, the participant is recommended to use precautionary measures against ultraviolet exposure (e.g., use of sunscreen, protective clothing and avoid sunbathing or using a solarium intensively)
	

**Table 6-9 Dose modifications for nazartinib (if capmatinib permanently discontinued and nazartinib continued as monotherapy)**

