Grade 1 (despite standard anti-emetics)	Recommendation: maintain dose level but adjust anti-emetic treatment
Grade 2 (despite standard anti-emetics)	Recommendation: omit dose until resolved to $\leq$ Grade 1, then resume at same dose level.

Worst toxicity CTCAEa Grade (value) during a cycle of therapy	Recommendations
	If vomiting returns as $\geq$ Grade 2, then suspend dose until resolved to $\leq$ Grade 1, then resume at $\downarrow$ 1 dose level
Grade 3 (despite standard anti-emetics)	Recommendation: omit dose until resolved to $\leq$ Grade 1, then resume at $\downarrow$ 1 dose level
Grade 4 (despite standard anti-emetics)	Recommendation: omit dose until resolved to $\leq$ Grade 1, then resume at $\downarrow$ 1 dose level
Dose modifications apply to participants who experience nausea and/or vomiting despite appropriate antiemetic medication. This medication should be started at the first sign of nausea and/or vomiting.	
SKIN AND SUBCUTANEOUS TISSUE DISORDERS	
Rash/photosensitivity Refer to Table 6-13 , Table 6-14 , and Table 6-15 for management and dose modification for rash/skin toxicities	
RESPIRATORY, THORACIC AND MEDIASTINAL DISORDERS	
Pneumonitis/Interstitial lung disease Refer to Table 6-16 for management and dose modification for non-infectious pneumonitis/interstitial lung disease	
GENERAL DISORDERS AND ADMINISTRATION SITE CONDITIONS	
Fatigue/ Asthenia	
Grade 1 or 2	May maintain dose level
Grade 3	Recommendation: omit dose until resolved to $\leq$ grade 1, then: If fully resolved in $\leq$ 7 days, then resume at same dose level If fully resolved in $>$ 7 days, then resume at $\downarrow$ 1 dose level
Metabolic	
Any Grade hypophosphatemia	Treatment with phosphate supplements as clinically indicated and maintain dose level
Persistent hyperglycemia (glucose $>$ 250 mg/dL) despite optimal anti-hyperglycemic therapy	Omit dose until hyperglycemia is adequately controlled then resume nazartinib at $\downarrow$ 1 dose level If adequate hyperglycemic control cannot be achieved with optimal medical management permanently discontinue nazartinib
Other adverse events	
Grade 1 or 2	May maintain dose level
Grade 3	Recommendation: omit dose until resolved to $\leq$ grade 1, then resume at $\downarrow$ 1 dose level

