Grade 4	Recommendation: omit dose and then discontinue nazartinib. Note: Omit dose for $\geq$ grade 3 vomiting or grade 3 nausea only if the vomiting or nausea cannot be controlled with optimal antiemetic (as per local practice)
All dose modifications should be based on the worst preceding toxicity. a Common Terminology Criteria for Adverse Events (CTCAE) version 5.0 b If Grade 3 or 4 hyper-bilirubinemia is due to the indirect (non-conjugated) component only, and hemolysis as the etiology has been ruled out as per institutional guidelines (e.g., Review of peripheral blood smear and haptoglobin determination), then $\downarrow$ 1 dose level and continue treatment at the discretion of the investigator. c LFTs include albumin, ALT, AST, total bilirubin (fractionated if total bilirubin $>$ 2.0 x ULN), alkaline phosphatase (fractionated if alkaline phosphatase $>$ 2.0 x ULN) and gamma-glutamyl transpeptidase (GGT). For isolated elevations of any grade of alkaline phosphatase and/or GGT, maintain dose level. d "Combined" defined as: total bilirubin increases to the defined threshold concurrently with ALT/AST increase to the defined threshold	

Worst toxicity CTCAEa Grade (value) during a cycle of therapy	Recommendations

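### Table 6-9 (nazartinib alone) has no eye rows and no pointer to those of Table 6-7, so retinal vein occlusion loses the permanent stop at Grades 1 to 3 and the ophthalmology referral at every grade

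*Protocol*

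**What the plan says.** Section 6.3.1 of the protocol contains three dose-modification tables. Table 6-7 covers nazartinib and capmatinib, Table 6-8 capmatinib alone, and Table 6-9 nazartinib alone.

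Table 6-7 has an eye-disorders block. Its row for retinal vein occlusion applies to any grade and reads "Permanently discontinue nazartinib and refer the participant to an ophthalmologist immediately for monitoring". Restarting nazartinib after recovery to Grade 1 or less "may be considered if approved by ophthalmologist and after documented discussion with Novartis". For the partner drug the row says "Resume capmatinib at same dose level upon resolution to" Grade 1 or less. The same block sets ophthalmic monitoring for uveitis/retinopathy and for other ocular toxicity: at least every 14 days at Grade 1 or 2, and at least weekly at Grade 3. It stops nazartinib when a Grade 3 event takes more than 14 days to resolve. For uveitis/retinopathy the wording is "then permanently discontinue participant from nazartinib and resume capmatinib at same dose level".

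The title of Table 6-9 gives its scope: "Dose modifications for nazartinib (if capmatinib permanently discontinued and nazartinib continued as monotherapy". Its headings are hematological, renal, hepatic, metabolic (twice), HBV/HCV, cardiac, vascular (hypertension only), gastrointestinal, skin, respiratory, general, and other adverse events. It sends the reader to other tables for HBV/HCV, rash and pneumonitis. Neither a row nor a footnote mentions the eye.

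**The concern.** The Table 6-7 row treats retinal vein occlusion as a nazartinib toxicity, because it stops nazartinib and brings capmatinib back at an unchanged dose. Losing capmatinib is therefore no reason to relax the rule. Yet the eye block appears only in the combination table and drops out when the implicated drug is the one that continues.

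A site that follows Table 6-9 as written could keep a participant on nazartinib through a Grade 1 or 2 retinal vein occlusion. It could also restart nazartinib after a Grade 3 event. In neither case would the table call for an ophthalmologist. This is a participant-safety gap in the rules, not a threat to the efficacy analysis.

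**Working it through.** No figure is stated and no arithmetic applies. The check sets the two tables side by side and then asks whether the Table 6-9 setting can be reached.

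**1. Which Table 6-9 row applies.** Retinal vein occlusion matches none of the named headings, and the only vascular row is hypertension. It falls to the row for other adverse events.

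**2. Action on nazartinib for retinal vein occlusion, by grade.** Which grades can be assigned to this event depends on CTCAE, which the protocol does not reproduce. All four grades in the Table 6-9 row are shown.

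| Grade | Table 6-7 | Table 6-9, other adverse events | Lost |
|---|---|---|---|
| 1 or 2 | Permanent stop, immediate referral, gated restart | "May maintain dose level" | Stop, referral, gate |
| 3 | As above | "Recommendation: omit dose until resolved to" Grade 1 or less, then one level lower | Permanent stop, referral, gate |
| 4 | As above | "Recommendation: omit dose and then discontinue nazartinib" | Referral (the stop is kept) |

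At Grade 3 Table 6-9 still interrupts dosing and lowers the restart dose. At Grade 4 the dose action survives, but no referral is stated.

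**3. Uveitis/retinopathy and other ocular toxicity.**
- Grade 1 or 2: both tables keep the dose. Table 6-9 omits the monitoring.
- Grade 3 resolving within 14 days: both tables resume nazartinib one level lower. Table 6-9 omits the weekly monitoring.
- Grade 3 taking longer than 14 days: Table 6-7 stops nazartinib. Table 6-9 has no such limit and resumes one level lower.
- Grade 4: both tables discontinue. Table 6-9 states no referral.

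**4. Whether participants can reach Table 6-9.** Four Table 6-7 rows permanently stop capmatinib and let nazartinib go on:
- febrile neutropenia taking more than 7 days to resolve;
- Grade 4 serum creatinine;
- Grade 4 amylase/lipase;
- Grade 4 peripheral edema, which names nazartinib monotherapy outright.

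**5. Who is exposed.** The Amendment 07 rationale says nobody in Phase Ib or Groups 1 to 4 is still on treatment. That leaves Group 5, planned at approximately 30 (Section 4.1). Within it, only those who progress on capmatinib, choose the combination (Section 6.1.2) and then lose capmatinib permanently come under Table 6-9.

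**The case against.** The best counter-argument is that Table 6-7 may never lapse. The text of Section 6.3.1 names Table 6-7 for interruption and re-initiation of both drugs and does not mention Table 6-9. Several Table 6-7 rows also direct stretches of nazartinib alone. A site could reasonably let a specific retinal vein occlusion row override a generic one. That reading is possible, but the title of Table 6-9 describes exactly this setting, the table has its own catch-all row, and it cross-refers elsewhere when it wants to borrow a rule. A protocol should not leave the choice to the site.

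Section 6.3.1 also has general safeguards. Single-drug treatment is described as exceptional and follows discussion with the sponsor. A drug-related interruption beyond 21 days ends treatment. Recurrence at the same or worse severity after a dose reduction does too. Each of these limits the harm, but none restores the permanent stop or the referral. The interruption rule cannot act at Grade 1 or 2, where dosing need not be interrupted. The local-practice clause covers only events that the protocol and its reference guidance leave out, and this event is in Table 6-7.

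Some stronger readings are tempting but unsupported:
- A reader might infer that the protocol obliges dosing through a retinal vein occlusion. The Grade 1 or 2 wording is permissive, and the investigator can stop treatment at any time.
- A reader might subtract the 14-day rule from the 21-day rule to get an exact window in which Grade 3 eye events are handled differently. The first counts time to resolution and the second counts from the next scheduled dose, so the difference is not a defined window.
- A reader might count Grade 3 or worse pancreatitis as a further route. That note stops capmatinib but is silent on whether nazartinib continues. The febrile neutropenia row is itself mixed, since a later bullet brings capmatinib back, but its instruction for resolution beyond 7 days is explicit.
- A reader might conclude that Table 6-9 is laxer throughout. It is not: it discontinues nazartinib at Grade 3 creatinine, where Table 6-7 resumes it at the same dose.

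**Conclusion.** The gap is real on the text reviewed, and minor. For retinal vein occlusion, Table 6-9 drops the permanent stop and the approval-gated restart at Grades 1 to 3, and states no ophthalmology referral at any grade. At Grade 4 the stop is kept. The ophthalmic monitoring of other eye events and the Grade 3 limit of 14 days are also absent.

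Reach is a subset of about 30 participants, and the protocol gives no rate for these events, so no expected count can be stated.

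The conclusion rests on two assumptions. The first is that Table 6-9 governs once capmatinib is permanently stopped, as its title says. The second is that no later section supplies the missing eye rules. The text reviewed ends at the start of Section 6.3.2, so Section 6.3.4 and Table 6-16 (toxicity follow-up evaluation) could not be read. Table 6-9 cites Table 6-16 only for pneumonitis and interstitial lung disease. A reader might infer that the protocol nowhere involves an ophthalmologist for nazartinib alone, but that cannot be claimed without those sections.

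**What to change.** First check whether Section 6.3.4 or Table 6-16 already carries the eye rules into nazartinib monotherapy. If not, take one of two routes at the next amendment:

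- **Copy the rows.** Add an eye section to Table 6-9 with the nazartinib actions and referrals of Table 6-7. For retinal vein occlusion of any grade, this means a permanent stop, immediate referral and the same gated restart. For uveitis/retinopathy and other ocular toxicity, it means the same monitoring intervals, the Grade 3 stop when resolution exceeds 14 days, and the Grade 4 referral.
- **Cross-refer.** Add a line to Table 6-9 saying that the eye-disorder rows of Table 6-7 continue to apply to nazartinib, as the table already does for HBV/HCV, rash and pneumonitis.

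Either route is an edit to one table. It adds no visit, test or procedure beyond those Table 6-7 already names, and leaves the sample size and analysis untouched.

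### Table 6-7, eye rows: some Grade 4 events are handled less strictly than Grade 3 events that resolve slowly (capmatinib for other ocular toxicity; nazartinib for uveitis/retinopathy and other ocular toxicity)

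*Protocol*

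**What the plan says.** Table 6-7 sets the dose changes for the combination. Under its footnote, the worst grade reached decides.

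Other ocular/visual toxicity:
- Grade 3 resolving within 14 days: capmatinib returns unchanged and nazartinib one level lower.
- Grade 3 resolving in more than 14 days: "then discontinue participant from nazartinib and resume capmatinib ↓ 1 dose level". No route back to nazartinib is given.
- Grade 4: "Permanently discontinue nazartinib, omit capmatinib and refer the participant to an ophthalmologist immediately for monitoring. Resumption of nazartinib at ↓ 1 dose level" may be considered after resolution to grade 1 or lower, "if approved by ophthalmologist and after documented discussion with Novartis". For capmatinib: "Resume capmatinib at same dose level upon resolution to ≤ grade 1", with no condition on time.

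Uveitis/retinopathy:
- Grade 3 resolving within 14 days: "then resume capmatinib at same dose level and nazartinib at ↓ 1 dose level".
- Grade 3 resolving in more than 14 days: "then permanently discontinue participant from nazartinib and resume capmatinib at same dose level".
- Grade 4: "Permanently discontinue nazartinib and refer the participant to an ophthalmologist for monitoring. Resumption of nazartinib following resolution to ≤ grade 1 may be considered", under the same two approvals. Capmatinib returns unchanged.

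Retinal vein occlusion of any grade is worded almost identically to Grade 4 uveitis: "Permanently discontinue nazartinib and refer the participant to an ophthalmologist immediately for monitoring. Resumption of nazartinib following resolution to ≤ grade" 1.

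Section 6.3.1 adds three general rules. An interruption of more than 21 days for drug-related toxicity ends study treatment unless the protocol says otherwise. Re-escalation is barred outside Tables 6-14 and 6-15. Exceptions may be agreed case by case with the sponsor.

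**The concern.** A dose-modification table should not become more lenient as the event gets worse. Here it does so in two ways.

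(a) For other ocular toxicity, the same slow recovery brings capmatinib back one level higher if the event peaked at Grade 4 than if it peaked at Grade 3.

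(b) For both uveitis/retinopathy and other ocular toxicity, nazartinib may be restarted after Grade 4, under approval, but not after a Grade 3 event that took more than 14 days to resolve.

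These events can threaten sight, and sites will follow the cell that matches the peak grade. Because re-escalation is generally barred, the dose gap created at restart would persist. What is at stake is consistent, safe dosing guidance, not an estimate or a decision rule.

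**Working it through.** No sample size, power or error rate is involved and the plan has no figure to reproduce. The check is a cell-by-cell reading of the eye rows in Table 6-7, with doses from Table 6-5 (capmatinib 400, 300, 200 mg b.i.d.) and Table 6-6 (nazartinib 100, 75, 50 mg q.d.).

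| Event | Branch | Capmatinib on restart | Nazartinib |
|---|---|---|---|
| Uveitis/retinopathy | Grade 3, ≤14 days | same level | one level lower |
| Uveitis/retinopathy | Grade 3, >14 days | same level | stopped, no restart route |
| Uveitis/retinopathy | Grade 4 | same level | stopped, gated restart, level not stated |
| Retinal vein occlusion | any grade | same level | stopped, gated restart, level not stated |
| Other ocular | Grade 3, ≤14 days | same level | one level lower |
| Other ocular | Grade 3, >14 days | one level lower | stopped, no restart route |
| Other ocular | Grade 4 | same level | stopped, gated restart one level lower |

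**Capmatinib.** Six of the seven branches keep the level and one lowers it: slow Grade 3 other ocular toxicity. Take an other-ocular event that resolves on day 16.
- From 400 mg b.i.d.: peak Grade 3 gives 300 mg b.i.d. (2 × 300 = 600 mg/day); peak Grade 4 gives 400 mg b.i.d. (2 × 400 = 800 mg/day). The worse event receives 200 mg/day more.
- From 300 mg b.i.d.: peak Grade 3 gives 200 mg b.i.d. (400 mg/day); peak Grade 4 gives 300 mg b.i.d. (600 mg/day). This case can arise because Section 6.1.1 carries the monotherapy dose of capmatinib into the combination.

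In the uveitis rows capmatinib returns unchanged after every branch, so it is not inverted there.

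**Time window.** The slow Grade 3 branch needs resolution after day 14. If the 21-day limit applies, an interruption beyond day 21 ends study treatment whatever the grade. The capmatinib inversion then exists for resolution on about days 15 to 21. If the Grade 3 and Grade 4 eye cells count as cases where the protocol says otherwise, there is no upper limit. The text does not settle this.

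**Nazartinib.** Restart is open in five branches and closed in two, and the two closed ones are the slow Grade 3 branches. In each event type, Grade 4 therefore has a route that slow Grade 3 lacks. Where the restart level is stated (three of the five), it is one step down, so 75 mg q.d. from 100 mg q.d. Retinal vein occlusion has one cell for all grades, so it has no inversion.

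**The case against.** The strongest reply is that Section 6.3.1 presents Table 6-7 as recommendations and allows case-by-case exceptions, so sponsor and investigator can correct an odd result. That flexibility is real, but an exception clause permits departures from a rule. It does not make a rule right when the rule gives the worse event the higher dose.

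A second reply is that slow Grade 3 other ocular toxicity is the only branch that lowers capmatinib, so that cell may be the mistake. This stands: the text does not show which cell is wrong. Table 6-8 runs the conservative way in its row for other adverse events (one level lower at Grade 3, permanent stop at Grade 4). It has no eye rows and covers capmatinib alone, so it is only weak support. Either correction removes the capmatinib inversion.

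A third reply is the 21-day limit. It may narrow the capmatinib inversion to about a week of resolution times, but it does not remove it.

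A reader might also infer two stronger points.
- One is that the cells for Grade 4 uveitis, retinal vein occlusion and Grade 4 other ocular toxicity contradict themselves by ordering a permanent stop and then allowing a restart. They can fairly be read as a default stop with a gated exception. Elsewhere Table 6-7 marks absolute stops as mandatory, and these cells do not. A site cannot restart on its own, so it does not face two competing orders. The wording is loose, no more.
- The other is that the unstated nazartinib restart level in two cells is an error. The level can be set in the sponsor discussion that any restart already requires.

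**Conclusion.** The point holds as a minor inconsistency in dosing guidance. As written, Grade 4 is treated less strictly than slow-resolving Grade 3 for capmatinib in other ocular toxicity (400 against 300 mg b.i.d. from full dose), and for nazartinib restart in both uveitis/retinopathy and other ocular toxicity.

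The capmatinib conclusion rests on the peak grade deciding the row, as the table footnote says, and on resolution after day 14. Its upper time limit depends on whether the 21-day rule applies.

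Reach is small. Amendment 07 records nobody on treatment in Phase Ib or Groups 1 to 4, so the rule now bears on Group 5 participants who progress on monotherapy and take the optional nazartinib add-on. That is some part of about 30 planned participants, or about 10 if the group stops after Stage 1. The text at hand gives no ocular event rate, so an expected number of cases cannot be stated.

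It would be wrong to infer an overdose or an effect on the results. No restart exceeds capmatinib 400 mg b.i.d., and no primary analysis, sample size or error rate is touched.

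**What to change.** **Capmatinib.** In the Grade 4 other ocular cell, resume one dose level lower, at least when resolution takes more than 14 days. If the sponsor judges the slow Grade 3 cell to be the error, resume at the same level there instead.

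**Nazartinib.** Choose one:
- delete the resumption sentence from the two Grade 4 cells (uveitis/retinopathy and other ocular); or
- give slow Grade 3 of both kinds the same gated restart, one dose level lower.

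Rewording the Grade 4 cells alone is not enough, because slow Grade 3 would remain a final stop.

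**Wording, secondary.** Wherever a gated restart is kept, replace the order to stop permanently with an order to omit, and state one dose level lower in the Grade 4 uveitis and retinal vein occlusion cells.

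Capmatinib in the uveitis rows can stay. It would also help to say whether the 21-day limit overrides these cells.

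The cost is the wording of a few table cells at the next amendment, with no change to the design or the analyses.
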